8.1 Screening Visit

See Table 1 for the procedures and assessment to be performed during the screening visit of the study. Screening visit can take place within 7 days before or after coronary angiogram. All screening visit test and procedures will occur upon signing the informed consent form (ICF). No screening exams will take place until the subject is fully informed of the research and signs the consent form.

A subject may be rescreened based on the Investigators judgement and will at a minimum need to reconsent and complete screening laboratory tests. The subject will remain with the same subject number throughout this process.

If any of the screening assessments (coronary angiogram, vasoreactivity testing, OCT, physical exam, labs, EKG, etc.) were performed as “Standard of Care” within 7 days of signing ICF, those results may be extracted from patient medical records and used for the screening visit in this study.

8.2 Baseline and Day 0 Visit

See Table 1 for the procedures and assessment to be performed during the baseline visit of the study. This visit will occur after all screening tests are completed and it has been determined that the subject meets eligibility criteria. This visit should occur within 0 - 30 days post-coronary angiogram.

See Table 1 for the procedures and assessment to be performed during the Day 0 visit of the study. The Day 0 visit will occur within 0 - 30 days post-coronary angiogram after all baseline tests are completed and it has been determined that the subject remains eligible. Once the subject is deemed eligible to continue in the study, the subject will be administered the investigational product. Refer to Appendix 1 for Infusion Guidelines.

8.3 Week 2, Month 1, Month 3, Month 6, and Month 12 (Post-Infusion Visit)

See Table 1 for the procedures and assessment to be performed for the Week 2, Month 1, Month 3, Month 6, and Month 12 study visits. Subjects who had a stent placed at screening will have a follow up coronary angiography at 6 months post-investigational product infusion to evaluate the treated lesion lumen loss with quantitative coronary angiography (QCA), physiology with fractional flow reserve (FFR) and endothelial function with coronary flow reserve (CFR). Outpatient visits should be completed as close to the scheduled visit dates as possible. There will be a window of ± 5 days for week 2 and ± 2 weeks for the Month 1, 3, 6, and 12 study visits.

An optional sub-study will be conducted on at least 5 participants from each treatment group in which they will undergo a bone marrow biopsy at Month 3 for a detailed molecular (genomic, proteomic, proliferation, senescence and differentiation assays) and functional assessment (angiogenic assays) of the effect of allogeneic MSCs on bone marrow derived autologous MSC and EPCs. All subjects will be asked to sign a separate ICF before participating in this optional sub-study. Due to the blinded nature of the study, more than 10 subjects will be enrolled in this sub-study and Cell Manufacturing lab will inform the clinical team once 5 subjects from each treatment complete the bone marrow biopsy. In the interest of participant safety, the bone marrow biopsy may be performed under ultrasound guidance (X-Ray or Ultrasound) by interventional radiology department, if indicated by investigator's clinical judgement.

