2.2 Study Endpoints

2.2.1 Primary Endpoints (Efficacy)

- Change in Brachial artery FMD% assessed at 2 weeks, 1-, 3-, and 6-months post-infusion compared to baseline.
- Change in EPC-CFUs at 2 weeks, 1-, 3-, and 6-months post-infusion compared to baseline.

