2.2.2. Secondary Endpoints

Efficacy:

- Cardiac catheterization angiography, CFR and FFR measurement to assess post-coronary angiography coronary artery endothelial function at 6 months post-infusion
- Target lesion lumen loss by QCA at 6 months post-infusion
- Endothelialization and stent site vessel healing parameters by OCT (only applicable if participant undergoes PCI).
- Circulating angiogenic and inflammatory markers at 1-, 3-, and 6-months post-infusion.
- Seattle Angina Questionnaire (SAQ) Angina Frequency and Quality of Life scales at 1-, 3-, and 6-months post-infusion.

Safety:

- Incidence (at one (1) month post-infusion) of any treatment-emergent serious adverse events (TE-SAEs), defined as the composite of: death, non-fatal MI, stroke, hospitalization for heart failure, sustained ventricular arrhythmias (characterized by ventricular arrhythmias lasting longer than 30 sec or with hemodynamic compromise) or atrial fibrillation.

- Incidence of Major Adverse Cardiac Events (MACE), defined as the composite incidence of (1) death, (2) hospitalization for cardiovascular events, or (3) non-fatal MI at 12 months.
- Treatment emergent adverse event (AE) and serious adverse event (SAE) rates through the duration of the study.
- Target Vessel Failure (revascularization, death, or MI attributed to the target vessel) post-PCI (only applicable if participant undergoes PCI).
- Abnormal hematology and clinical chemistry value results.

Exploratory:

- Detailed molecular and functional assessment (genomic, proteomic, proliferation, senescence and differentiation, and angiogenic assays) of bone marrow aspirate at 3 months post-infusion.

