2. A physical examination will be performed and may include the following examinations: general appearance; skin and nails; limbs; head, eyes, ears, nose, throat (HEENT) and neck; respiratory; cardiovascular; and abdominal. Vital Signs measurements will consist of: height, weight, heart rate, blood pressure, respiratory rate, oxygen saturation, and temperature. Height is only required at screening. If physical exam and vitals were performed as “Standard of Care” within 7 days of signing ICF, those results may be extracted from patient medical records and used for the screening visit in this study. The screening visit physical exam can be completed by the participants’ treating physician.
3. Concomitant medications will be recorded at screening visit and updated at each visit.
4. Randomization can be performed within 7 days prior to IP infusion.
5. Refer to Appendix 1 for Infusion guidelines.
6. Refer to hospital protocols for coronary angiogram guidelines. Results from the screening cardiac catheterization may be extracted from patient medical records and used for the purposes of this study. Subjects who did not have a stent placed at screening will not undergo the coronary angiogram (and associated measurements) at Month 6, but should complete the other assessment listed on Time and Events Table, per investigator’s judgement.
7. Subjects who did not have a stent placed at screening may still undergo the coronary angiogram (and associated measurements) at Month 6, but should complete the other assessment listed on Time and Events Table. All procedures (CFR, FFR, IFR, IVUS, and/or OCT) will be performed in accordance with the established hospital protocols which are done as “Standard of Care”. Subjects who undergo PCI at screening should have CFR, FFR, IFR, IVUS, and/or OCT measurements if available, as per investigator’s judgement.
8. Refer to Appendix 2 for Brachial Ultrasound (Brachial Artery Ultrasound to assess endothelial function must be performed prior to 12pm).
9. Bone Marrow Biopsy will be performed at month 3 visit. Separate ICF will be used for this optional sub-cohort. The bone marrow biopsy can be performed in the Catheterization Laboratory or in Interventional Radiology department, either with or without imaging guidance (X-Ray or Ultrasound).
10. All subjects will be asked to complete the Seattle Angina Questionnaire (SAQ), EQ-5D, and SF-36 quality of life questionnaires. Only male subjects will be asked to

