These samples will 1) provide storage of critical biomaterials derived from subjects enrolled in ACESO IHD 2) provide long-term integrity of these biospecimens and samples, and 3) provide management of samples for postdoctoral studies of immunologic, immunohistochemical, cellular, and molecular analyses of collected samples; as well as cell-surface markers (CXCR4, C-Kit, & Connexin 43), transcriptomic/Proteome (DNA, RNA, miRNA, protein samples, and telomerase, akt), growth factors (Sdf-1, notch,), functional Assays (cell growth rate, VEGF, and CFU assay), CD3, CD25, CD69, Inflammatory (IL-1, TGF-) , (but not limited to these biospecimens) will be used for research purposes only, will be stored without personal identifying information, and will be shared with approved researchers who will conduct studies to improve the understanding of the effects of cell therapies and/or of Type 2 DM.

Endothelial Progenitor Cell-Colony Forming Units (EPC-CFUs) Assay

Blood collection for EPC-CFU assay will be performed to assess endothelial function at baseline, week 2 and 1-, 3-, and 6-months post study product infusion. This will help provide cumulative data in assessing whether stem cell infusion improves endothelial function. Blood collection for EPC-CFU assay will be performed in the morning prior to 12pm.

Fresh blood will be processed for cell culture assays for endothelial progenitor stem cells colonies counting (a 5 days' protocol). Fifty milliliter of blood will be processed; peripheral-blood mononuclear cells will be isolated by Ficoll density-gradient centrifugation, will be washed twice in phosphate buffered saline with 5% fetal bovine serum and re-suspended in media (EndoCult basal media with supplements; StemCell Technologies, Vancouver, British Columbia, Canada) for EPC colony-forming assay. Cells will be planted on human fibronectin-coated plates (BIOCOAT; Becton Dickenson Labware, Bedford, Massachusetts) at a density of 5×10^6 cells/well and incubated at 37°C in humidified 5% CO₂. After 48 hours, the non-adherent cells will be re-plated onto fibronectin-coated 24 well plates at a density of 1×10^6 cells/well. After 5 days, colony forming units (defined as a central core of rounded cells surrounded by elongated and spindle-shaped cells) will be counted manually in 8 wells out of a 24-well plate. Refer to SOP ISCI QAL-006 (Collection and Transport of Blood Specimens for Clinical Research) and SOP ISCI QAL-007 (EPC Protocol).

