APPENDIX 2: Flow Mediated Diameter percent change (FMD%) Instructions

A Flow Mediated Diameter percent change (FMD%) will be performed four times during the study: at baseline, Week 2, Month 1, 3, and 6 follow-up visits. This exam will assess vascular function.

Participant should be instructed in pre-session requirements prior to the session. These requirements include:

- a) no coffee, tea, soda or other caffeinated beverages in the 4 hr preceding session;
- b) no smoking cigarettes or tobacco use in the 2 hr preceding session;
- c) no alcohol since midnight;
- d) no exercise in the 4 hr preceding session;
- e) for men, no use of erectile function medicines in the 24 hr preceding the session;
- f) wear a short sleeve shirt for the session.

Procedure Details:

- All measurements of the brachial artery diameter and FMD will be performed in the morning, in a quiet and dark room and at controlled ambient temperature.
- Studies will be conducted after an overnight fast of at least 10 hours (water is permitted), with the subject supine and after 10 minutes of rest.
- The subject's right arm will be comfortably immobilized in an extending position, allowing for ultrasound scanning of the brachial artery 5–10 cm above the antecubital fossa.
- Blood flow is manipulated in the brachial artery by a pneumatic cuff placed around the forearm distal to the segment of artery being imaged inflated to a suprasystolic pressure (240 mm Hg) for 5 min and released, resulting in a brief episode of reactive hyperemia. Changes in brachial artery diameter in response to the increase in blood flow once the forearm cuff is deflated are recorded.
- Recovery of brachial artery diameter is assessed for an additional 5 min. Images are all digitized and stored on portable storage device following recording for later off-line scoring.
- Two repeated tests are performed. An inter-test rest period of 5 min is used and the second test is not conducted until mean arterial pressure is within 5 mmHg of the initial resting mean arterial pressure taken following the initial rest period.
- Recordings are digitized continuously for 5 min of baseline recording, 5 min of cuff inflation to supra-systolic pressure, and for 5 min after cuff deflation when brachial flow increases to accommodate the dilated resistance vessels.

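### Month 6 FMD%, EPC-CFU, markers and SAQ have no set order relative to the protocol's own angiogram, and FMD is fixed to the right arm although arterial access is unspecified

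*Combined protocol and SAP*

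**What the plan says.** **Shared visit.** Section 8.3 states that "Subjects who had a stent placed at screening will have a follow up coronary angiography at 6 months post-investigational product infusion". Table 1 lists the angiogram and its physiology and imaging measurements, the brachial ultrasound, the questionnaires, the biomarkers and the EPC-CFU draw in one Month 6 column. The window is plus or minus "2 weeks for the Month 1, 3, 6, and 12 study visits".

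**Endpoints affected.** Both primary endpoints in section 2.2.1 include Month 6: "Change in Brachial artery FMD% assessed at 2 weeks, 1-, 3-, and 6-months post-infusion compared to baseline" and "Change in EPC-CFUs at 2 weeks, 1-, 3-, and 6-months post-infusion compared to baseline". Among the secondary endpoints in 2.2.2 are the circulating markers and "Seattle Angina Questionnaire (SAQ) Angina Frequency and Quality of Life scales at 1-, 3-, and 6-months post-infusion".

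**Timing rules.** For FMD, Table 1 note 8 says "Brachial Artery Ultrasound to assess endothelial function must be performed prior to 12pm", and Appendix 2 adds a fast of at least 10 hours and a list of things to avoid beforehand. For EPC-CFU, section 8.4.5 says "Blood collection for EPC-CFU assay will be performed in the morning prior to 12pm". The SAQ has no rule within the visit. None of these rules mentions the angiogram.

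**Arm and access.** Appendix 2 says that the subject's "right arm will be comfortably immobilized in an extending position" and gives no alternative. Table 1 note 6 refers angiogram technique to hospital protocols, and access site is not mentioned anywhere.

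**Who is exposed.** For subjects without a stent, Table 1 note 6 rules out the Month 6 angiogram and note 7 permits it.

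**Baseline.** Section 8.2 allows the baseline visit 0 to 30 days after the index angiogram.

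**The concern.** A schedule that follows the protocol exactly can place the angiogram first and take FMD, EPC-CFU, markers and SAQ afterwards. A primary endpoint would then be read on a recently catheterised patient. Where the angiogram prompts a repeat intervention, the SAQ would be read after that intervention. The protocol's own background (section 1.1) cites a meta-analysis in which routine follow-up angiography went with more target lesion revascularisation (OR 1.73, 95% CI 1.42 to 2.11), so this route is not remote.

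The right-arm rule adds a local problem. If the right arm was used for access, FMD is imaged in the instrumented limb. That can happen at Month 6, and it can happen at baseline, which enters all four change scores.

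Appendix 2 already controls caffeine, tobacco, alcohol, exercise and erectile-function medicines before FMD. Saying nothing about a catheterisation that the protocol itself schedules is a gap by that standard. Sections 6.6, 10.1 and 10.2 describe neither stratification by stenting nor covariate adjustment that might absorb part of the effect.

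**Working it through.** The plan gives no power, effect size or SD (section 10.1), so there is no stated figure to reproduce. The check has two parts.

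**1. What the text permits.** One window of plus or minus 14 days covers all Month 6 procedures, a span of 28 days. With no order, a measurement may fall anywhere from 28 days before to 28 days after the angiogram. The pre-noon rule and the 10-hour fast make FMD later on the same day unlikely, but they do not exclude the next morning. The SAQ may be taken on the same day.

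**2. Scale, on assumptions.** From the documents: 30 subjects, 15 per arm, two-sided alpha 0.05. Assumed, because the documents are silent:
- 15 subjects have the Month 6 angiogram (range 10 to 20).
- Half of them are measured after it.
- FMD is lowered by b = 2 points in those subjects (range 1 to 4).
- The SD of the analysed Month 6 value is 3 points.

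The affected share is f = (number exposed / 30) × 0.5. This is 0.25 in the central case and 1/6 to 1/3 over the range.

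- Shift in the overall Month 6 mean, f × b: 0.25 × 2 = 0.5 point. Range: 1/6 × 1 = 0.17 to 1/3 × 4 = 1.33. This shift is common to both arms in expectation.
- Added variance, f(1 − f)b²: 0.25 × 0.75 × 4 = 0.75 points squared, or 0.75/9 = 8% of the assumed variance. Range: 1/6 × 5/6 × 1 = 0.14 to 1/3 × 2/3 × 16 = 3.6 points squared.
- Shift in the between-arm contrast if one arm has 3 more exposed subjects: (3/15) × 0.5 × 2 = 0.2 point (0.1 to 0.4 for b = 1 to 4).
- Standard error of the contrast: 3 × √(2/15) = 1.10 points. The shift is 0.2/1.10 = 0.18 SE.

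**Chance of imbalance.** With exactly 15 of 30 exposed, the arms differ by 3 or more with probability 1 − 2 × C(15,7) × C(15,8)/C(30,15) = 0.466. With exactly 10 or 20 exposed the difference must be even, so the corresponding event is 4 or more, with probability 0.245. If each subject is instead exposed independently, the probability of a difference of 3 or more is 0.36 at a 50% share and 0.29 at 25% or 75%.

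**Power.** With 15 per arm, the difference detectable with 80% power is (1.960 + 0.842) × √(2/15) = 1.02 SD. Suppose an artefact of b SD is present in 25% to 75% of patients, equally in both arms. The SD is then multiplied by √(1 + p(1 − p)b²), where p is that share, and power falls as follows:

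| Artefact | Power |
|---|---|
| 0.25 SD | 79–80% |
| 0.5 SD | about 78% |
| 1 SD | 71–73% |

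**The case against.** **The mechanism has no source in the documents.** No section says how far, in which direction or for how long catheterisation affects FMD, EPC-CFU or the markers. The calculation also applies the same artefact whether the measurement follows by hours or by four weeks. This stands, and the figures above are illustrations only.

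**Randomisation and blinding make the effect non-differential in expectation.** This also stands. A reader might infer that the Month 6 comparison of cells with placebo is biased. The documents do not support that: the mean shift cancels in expectation, and a chance imbalance is largely the same random error already counted as added variance.

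**The local arm problem is easily overstated.** A reader might infer that FMD is measured downstream of the puncture. Appendix 2 images the brachial artery 5 to 10 cm above the antecubital fossa, so a wrist or elbow puncture lies distal to the imaged segment. A catheter may pass through that segment, which is a different matter. With access unstated, right-arm exposure could be anything from none to frequent.

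**The consequence is limited.** Month 6 is one of four post-infusion time points, and the other three have no protocol angiogram. The SAQ is secondary. Section 10.2 calls efficacy exploratory. The trial is run at one center, and the specimen procedures cited in 8.4.5 are not available here.

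What remains is that the written right-arm rule and the open order permit a worse measurement than the same visit could deliver.

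**Conclusion.** The point holds as a modest, avoidable weakness in measurement. The documents establish the shared window, the missing order and interval, the fixed right arm and the unspecified access. They do not establish that any contamination will occur, or how large it would be.

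The likely harm is added noise at Month 6 and distorted within-arm change from baseline. Between-arm distortion arises only through chance imbalance in who has the angiogram: about 0.2 FMD point, or roughly 0.2 SE, for a 3-subject imbalance. That figure rests on an assumed 2-point artefact in half of those exposed and an assumed SD of 3. How many subjects are exposed cannot be settled while notes 6 and 7 disagree.

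The change is worth making because it costs almost nothing and 15 subjects per arm leave little precision to spare. It should not be read as undermining the trial.

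**What to change.** - **Table 1 and section 8.3:** require Month 6 FMD, EPC-CFU and biomarker blood and all questionnaires to be completed before any Month 6 angiogram.
- **Appendix 2:** replace the fixed right arm with the arm not used for arterial access at the index angiogram, kept the same at every visit.
- **Case report form:** record the arm imaged, the access site, and the dates of the angiogram and of each measurement, including the interval from the index angiogram to baseline.
- **Table 1 notes 6 and 7:** reconcile them on who has the Month 6 angiogram.

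This needs no extra visit, staff or procedure. The downside is slightly tighter Month 6 scheduling.

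One limit remains. Baseline still falls 0 to 30 days after the index angiogram, so systemic post-procedure effects on baseline FMD, EPC-CFU, markers and SAQ are not removed. The arm rule deals only with the local part, and the recorded interval only makes the rest visible. A matching rule for the optional Month 3 bone marrow biopsy is not proposed, since nothing examined here supports one.

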8.4 Assessment Details

8.4.1 Medical History and Physical Exam

A complete medical history will be conducted during screening testing including: vital signs, height and weight; medical, surgical, and smoking history; and review of current use of prescription and OTC medications. Physical exam performed by the treating physician can be used as part of the screening assessments. Similar physical exams will be conducted at each additional clinic visit during the study including vital signs, weight, review of AEs, and concomitant medications

8.4.2 Vital Signs

Vital sign measurements will be performed at least once on each study visit up to time of discharge. These measurements will consist of oxygen saturation, weight, respiratory rate, heart rate, blood pressure, and temperature. Height will only be collected at the screening visit.

8.4.3 Flow Mediated Diameter percent change (FMD%)

A Flow Mediated Diameter percent change will be performed four times during the study: at baseline, and at the Week 2, Month 1, 3, and 6 follow-up visits. This exam will assess systemic endothelial function. All measurements of the brachial artery diameter and FMD will be performed in the morning, in a quiet and dark room. (refer to appendix 3)

8.4.4 Coronary Angiography

Coronary angiography will be done by the interventional cardiologist 6 months after infusion of the investigational product to assess post-PCI coronary artery endothelial function, assessed by IFR, CFR, and/or FFR, as available. Participants will also have evaluation of target lesion lumen loss by IVUS or OCT, as available.

8.4.5 Laboratory Testing

Gene Expression

A separate blood sample of approximately 17mL for gene expression (DNA) profiling of WBC (at Day 0 OR Month 6 visit) and a separate blood sample of approximately 5.0mL for RNA expression analysis (at Day 0 AND month 6 visits) will be obtained from the study participants, as detailed on Table 1. All samples will be identified so that they can be linked to individual subjects. These samples may be stored indefinitely. Individual results will not be returned to the subject or the study physician. The samples will be linked to subjects, but there will be no recontact. Data presented in publications will not contain individual subjects' clinical characteristics or outcomes; only aggregate data from the entire study will be disclosed. Refer to SOP ISCI QAL-006 (Collection and Transport of Blood Specimens for Clinical Research).

Biomarkers/Immune Monitoring for Graft Rejection

The studies planned in this protocol will utilize allogeneic human bone marrow derived MSCs in subjects with endothelial dysfunction and ischemic heart disease due to the Type 2 DM. The use of an allogeneic graft raises the potential of graft rejection through immune cells resulting in failure of the therapy. MSCs are ideal candidates for allogeneic transplantation because they show minimal MHC class II and ICAM expression and lack B-7 co-stimulatory molecules necessary for T-cell mediated immune responses^{57, 58}. Indeed both types of cells do not stimulate a proliferative response from alloreactive T-cells even when the cells have differentiated into other lineages or are exposed to proinflammatory cytokines. Previous studies have demonstrated that MSCs have significant immunomodulatory effects, inhibiting T-cell proliferation, prolonging skin allograft survival, and decreasing graft-versus-host disease (GVHD). Recently human MSCs were shown to alter the cytokine secretion profile of dendritic cells, T cells, and natural killer cells in vitro, inhibiting secretion of proinflammatory cytokines (e.g. TNF α , IFN- γ) and increasing expression of suppressive cytokines (e.g. IL-10), possibly via a prostaglandin E2 mediated pathway.

In vivo studies of the fate of MSCs have shown that, when transplanted into fetal sheep, human MSCs engraft, undergo site-specific differentiation into various cell types, including myocytes and cardiomyocytes, and persist in multiple tissues for as long as 13 months after transplantation in non-immunosuppressed immunocompetent hosts. Further, in vivo studies using rodents, dogs, goats, and baboons demonstrate that allogeneic MSCs can be engrafted into these species without stimulating systemic alloantibody production or eliciting a proliferative response from recipient lymphocytes. These findings, coupled with our demonstration of efficacy of these cells for cardiac repair, solidify the notion of using MSCs as an allograft for successful tissue regeneration.

As part of the ACESO IHD protocol we will obtain peripheral blood samples from all subjects to evaluate the presence of activated T cells. Two heparinized (green top) vacutainer tubes (approx. 15 cc total blood) will be collected at different time points during the study (Reference Table 1 for schedule). Peripheral blood mononuclear cells (PBMC) will be isolated from heparinized blood by Ficoll sedimentation and will be viably cryopreserved for planned assessments of T cell activation. Refer to SOP ISCI QAL-006 (Collection and Transport of Blood Specimens for Clinical Research).

Two of the best-accepted markers of T cell activation are CD69 and CD25 (IL-2 receptor). We could monitor the activation of T cells by flow cytometric analysis of

CD3+CD25+CD69+ cells in thawed PBMC. CD69 is an immediate/early marker of CD3+ T cell activation while CD25 expression increases within 1-2 days of activation and remains sustained over the intermediate-long term during chronic immune activation. Given the differences in the kinetics of CD69 and CD25 up regulation, assessment of both activation phenotypes (CD3+CD69+ and CD3+CD25+) will maximize the sensitivity of detection of T cell activation following allogeneic MSC infusion.

Additionally, in female subjects who receive allogeneic MSCs, the stored baseline serum can be analyzed to evaluate the antibody responses to HLA and H-Y antigens.

These samples will 1) provide storage of critical biomaterials derived from subjects enrolled in ACESO IHD 2) provide long-term integrity of these biospecimens and samples, and 3) provide management of samples for postdoctoral studies of immunologic, immunohistochemical, cellular, and molecular analyses of collected samples; as well as cell-surface markers (CXCR4, C-Kit, & Connexin 43), transcriptomic/Proteome (DNA, RNA, miRNA, protein samples, and telomerase, akt), growth factors (Sdf-1, notch,), functional Assays (cell growth rate, VEGF, and CFU assay), CD3, CD25, CD69, Inflammatory (IL-1, TGF-) , (but not limited to these biospecimens) will be used for research purposes only, will be stored without personal identifying information, and will be shared with approved researchers who will conduct studies to improve the understanding of the effects of cell therapies and/or of Type 2 DM.

Endothelial Progenitor Cell-Colony Forming Units (EPC-CFUs) Assay

Blood collection for EPC-CFU assay will be performed to assess endothelial function at baseline, week 2 and 1-, 3-, and 6-months post study product infusion. This will help provide cumulative data in assessing whether stem cell infusion improves endothelial function. Blood collection for EPC-CFU assay will be performed in the morning prior to 12pm.

Fresh blood will be processed for cell culture assays for endothelial progenitor stem cells colonies counting (a 5 days' protocol). Fifty milliliter of blood will be processed; peripheral-blood mononuclear cells will be isolated by Ficoll density-gradient centrifugation, will be washed twice in phosphate buffered saline with 5% fetal bovine serum and re-suspended in media (EndoCult basal media with supplements; StemCell Technologies, Vancouver, British Columbia, Canada) for EPC colony-forming assay. Cells will be planted on human fibronectin-coated plates (BIOCOAT; Becton Dickenson Labware, Bedford, Massachusetts) at a density of 5×10^6 cells/well and incubated at 37°C in humidified 5% CO₂. After 48 hours, the non-adherent cells will be re-plated onto fibronectin-coated 24 well plates at a density of 1×10^6 cells/well. After 5 days, colony forming units (defined as a central core of rounded cells surrounded by elongated and spindle-shaped cells) will be counted manually in 8 wells out of a 24-well plate. Refer to SOP ISCI QAL-006 (Collection and Transport of Blood Specimens for Clinical Research) and SOP ISCI QAL-007 (EPC Protocol).

